### **9.3.2 Potential Missing Data, Attrition and Premature Trial Endpoint**

We considered all potential causes of missing data and we developed strategies to minimize and mitigate them. In initial pilot studies, 34 of 177 (19%) QSM assessments in CA patients were unusable due to technical reasons (mostly patient movement during image acquisition). We eliminated this problem in the most recent 25 consecutive cases with specific patient instructions. We now implement a further step of reviewing the QSM acquisition, and rapidly processing it (10 minutes on local Matlab computer terminals in our laboratory). This allows us to repeat the QSM acquisition if needed, before proceeding with contrast injection for DCEQP measurements. This “chaperoned biomarker acquisition” reduces to virtually zero the rate of missing QSM measures (See letter by [name] and Protocol Section 6.5). We nevertheless project up to 10% missing biomarker data related to imaging (claustrophobia, etc.). We further project an additional 10% missing data due to imperfect follow-up, higher than that recorded in recent trials conducted by our teams (113, 114).

Up to 20% of subjects randomized to atorvastatin (10% of trial subjects) might not tolerate the 80 mg/day dose. Many will continue the drug at the lower dose. In fact, **serious side effects or intolerance of the lower dose are expected to result in attrition in less than 5% of cases**, per extensive meta-analyses of trial experience with the study drug (See Protection of Human Subjects; and Protocol section 7.3). Another **20-30% of cases might reach a prespecified study endpoint** because of SH, and they would also stop the drug before the end of the 2-years follow-up. All subjects who stop the drug, and those with non-compliance as defined, will still be followed for the full 2 years with scheduled clinical and imaging assessments, and will be included in the **primary analysis per intention-to-treat**.

To permit secondary analysis per treatment rendered, at the power and Type I error described above, we decided to **expand the sample size by an ample 37.5%, factoring the highest combined estimates of missing data and attrition.**

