## Sample Size and Population

The study is designed to include 80 subjects, randomized 1:1 to receive either atorvastatin or placebo. Randomization is stratified to insure a balanced treatment allocation by gender. The sample size was expanded by 37% to accommodate a highest possible estimate of missing data and potential attrition due to compliance, drug intolerance and safety endpoints, leaving at least 25 subjects in each of placebo and atorvastatin groups, which, per power calculations, are needed to detect a relevant difference in primary QSM biomarker. Subjects will be enrolled at the study investigator's institution where trial preparations have been optimized. Case referrals will be encouraged through a regional referral Chicago-wide academic and clinical consortium, and through the Angioma Alliance.

At midpoint of the trial, futility analysis is planned, and adaptive recalculation of sample size based on the actual observed primary outcome and treatment effect.

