## 9.3 Sample Size and Accrual

### 9.3.1 Sample size and Treatment Effect Estimation

Sample size calculations were based on providing sufficient power to test the primary hypothesis, that the proposed intervention impacts QSM biomarker activity (indicative of reduced or increased lesional bleeding) during 2 years of prospective follow-up after a recent CA SH. **The primary outcome is the mean % change in lesional QSM per year (called the change score).** Each patient contributes two outcome measurements (at year 1 and year 2, i.e. epochs). Evaluation of the intervention on this outcome will be performed as a time-averaged difference between two arms using a repeated measures analysis implemented as a linear mixed model and intention-to-treat principle (110).

**Estimating a “First-in-Man” treatment effect on a biomarker** can be difficult when such effect is demonstrated mechanistically but the translation to a human effect size remains unknown (111). Based on pilot data linking QSM change to clinical events, **we propose a minimum, clinically meaningful and mechanistically plausible treatment effect to be a 20% absolute difference in the mean change score.** It would be “a minimum expected effect”, <1/2 the mean 44% QSM increase observed with CA bleed or growth during longitudinal 1-year follow-up of previously stable lesions; and “clinically meaningful”, > 3X the threshold of QSM change associated with maximum sensitivity-specificity on ROC analyses (58). The absolute QSM effect size postulated herein is “plausible mechanistically”. It would be 0.0068 ppm [20% of 0.0340 ppm mean QSM change observed during follow-up of CA with SH (59)], 6-22 folds lower than the observed range of atorvastatin treatment effect on Perls stain intensity in *Ccm1* and *Ccm3* murine models (Figures 2, 3, 5).

One-year %QSM change in 16 pilot study patients (Figure 7), followed for either 1 or 2 years (22 patient-year epochs), was used to estimate the 1-year/patient standard deviation and within-patient correlation of the primary outcome in trial candidates. A sample size calculation was performed using a repeated measures analysis of two annual percent QSM change scores, assuming a two-tailed test, power = 0.9 and alpha = 0.05 (112). The actual within person correction from the pilot data was estimated at approximately -0.6 (Spearman); however, as this was based on only 6 patients with two-year’s

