worth of data, we chose the more conservative within person correlation of 0 for our sample size estimates. In addition, we assumed a common standard deviation of 30 for the mean percent change score, which to be conservative is about 20% larger than the standard deviation in our pilot data. **To detect a 20% absolute difference between the mean change score in each arm, based on two annual change scores measured per patient (at years 1 and 2), 25 patients per arm would be required.** To detect a smaller or larger effect size, an absolute difference of 15% or 25%, 44 or 17 patients per arm would be required, respectively (Hintze 2014, PASS v13, NCSS, Kaysville, Utah, USA [www.ncss.com](http://www.ncss.com)). The sample size was further expanded by 37.5% to accommodate the highest estimate of missing data from all causes as discussed below. Hence we shall aim to enroll **40 patients/arm, 80 total subjects.**

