### **Analysis of Treatment Compliance**

Treatment compliance is crucial to validate the study objectives. A compliance threshold of 90% will be implemented for proposed analyses per treatment rendered. Drug adherence will be rigorously monitored through an innovative electronic system that will provide continuously streamed real time data in addition to confirmatory manual pill count at each follow up call and scheduled visits. Assessment of compliance is an integral component at every scheduled or unscheduled evaluation and will be based on the **electronically acquired data as well as the missed doses log in the case report form (CRF)**. *A subject will be deemed noncompliant with the study intervention if he/she misses more than 21 consecutive doses at any point, or accumulate a log of 75 missed doses throughout the study.* Treatment compliance shall be compared in atorvastatin versus placebo cases as one of the secondary aims of the study.

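### The 37.5% allowance is not the highest combination of the losses listed in 9.3.2, so 25 per arm and 0.90 power for the treatment-rendered analysis are not supported at those losses

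*Combined protocol and SAP*

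**What the plan says.** Section 9.3.1 sizes the trial "assuming a two-tailed test, power = 0.9 and alpha = 0.05", for "a 20% absolute difference in the mean change score". On variability it says "we assumed a common standard deviation of 30 for the mean percent change score", with two annual scores per patient and a within-person correlation of 0. This gives 25 patients per arm. It continues: "The sample size was further expanded by 37.5% to accommodate the highest estimate of missing data from all causes", and arrives at 40 per arm.

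Section 9.3.2 lists the losses:
- up to 10% for imaging;
- a further 10% for imperfect follow-up;
- less than 5% attrition from serious side effects or intolerance of the lower dose;
- a separate 20-30% stopping drug because of symptomatic hemorrhage.

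It gives the purpose of the allowance as "To permit secondary analysis per treatment rendered, at the power and Type I error described above", and says the decision was to "expand the sample size by an ample 37.5%, factoring the highest combined estimates of missing data and attrition". No derivation of 37.5% is shown.

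The synopsis (Sample Size and Population) rounds the figure to 37%, says it also covers compliance, and describes the result as "leaving at least 25 subjects in each of placebo and atorvastatin groups".

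Sections 9.2 and 9.5 admit to the treatment-rendered analysis any patient with one annual epoch or more. The part of 9.5 on treatment compliance sets a 90% threshold for that analysis and calls a subject noncompliant who, among other criteria, "misses more than 21 consecutive doses at any point". No expected noncompliance rate is given.

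**The concern.** The plan makes three linked statements about the secondary analysis: the allowance is the highest combined loss, no fewer than 25 per arm remain, and power stays at 0.90. A reader who combines the listed components at their upper limits does not get 37.5% and does not keep 25 per arm.

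The word for the allowance is also wrong. Raising 25 by 37.5% gives 34.4, not 40. The enrolled number is right for a 37.5% loss but is described as a 37.5% expansion in three places.

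At stake is how a null or imprecise treatment-rendered result would be read. The plan would lead readers to credit that analysis with a precision that its own attrition figures do not guarantee. The primary analysis is not at stake, because 9.3.2 keeps patients who stop drug in follow-up and in the intention-to-treat analysis.

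**Working it through.** **Inputs.** From 9.3.1: difference 20, SD 30 per annual score, two scores, correlation 0, two-sided alpha 0.05, 25 required and 40 enrolled per arm. From 9.3.2: the four losses above, taking intolerance at its 5% bound. The same losses are applied to both arms.

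**Step 1: reproduce the plan.** The SD of a patient's mean score is 30/√2 = 21.2. The noncentrality is 20 / (21.2 × √(2/n)). At n = 25 it is 3.33, and a two-sample t test (2n − 2 degrees of freedom) has power 0.904; 25 is the smallest n reaching 0.90. The same method gives 44 and 17 for differences of 15 and 25, as stated. Then 25 / (1 − 0.375) = 40. The design figures reproduce.

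**Step 2: loss or expansion.** 40/25 = 1.60, a 60% expansion. 25 × 1.375 = 34.4. So 37.5% is the fraction that may be lost.

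**Step 3: combine the listed losses, removing lost patients whole.**

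| Hemorrhage | Combination | Loss | Left of 40 | Power |
|---|---|---|---|---|
| 20% | multiplied: 1 − 0.9 × 0.9 × 0.95 × 0.8 | 38.4% | 24.6 | 0.90 |
| 20% | added: 10 + 10 + 5 + 20 | 45% | 22 | 0.86 |
| 30% | multiplied: 1 − 0.9 × 0.9 × 0.95 × 0.7 | 46.1% | 21.5 | 0.86 |
| 30% | added: 10 + 10 + 5 + 30 | 55% | 18 | 0.79 |

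The degrees of freedom matter little. At 18 per arm, power is 0.785 counting patients and 0.797 counting epochs, hence about 0.79. All four rows leave fewer than 25, though the first keeps power at essentially 0.90.

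**Step 4: count epochs instead.** Section 9.3.3 speaks of 100 person-year epochs, or 50 per arm. If some patients who bleed keep their year-1 epoch, each of them loses one epoch rather than two. With hemorrhage at 30%, out of 80 epochs per arm:

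- Half of those who bleed keep year 1. Added: 80 × (1 − 0.25 − 0.225) = 42 epochs. Multiplied: 80 × 0.9 × 0.9 × 0.95 × 0.775 = 47.7. Power is about 0.85 to 0.89.
- All of them keep year 1. Added: 80 × (1 − 0.25 − 0.15) = 48 epochs. Multiplied: 80 × 0.9 × 0.9 × 0.95 × 0.85 = 52.3. Power is about 0.89 to 0.92.

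**Step 5: primary analysis.** Imaging and follow-up losses of 20% leave 32 per arm, with power about 0.96.

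**The case against.** The plan states no rule for combining losses, and the causes may overlap in the same patient. Multiplied, with hemorrhage at the bottom of its range, they leave 24.6 per arm and power of about 0.90, which is in effect what the plan claims. Heavier overlap could bring the loss to 37.5% or below. This stands as a limit on the size of the shortfall. It does not rescue the description of 37.5% as the highest combination, and the wording of 9.3.2, which presents the follow-up and hemorrhage losses as further to those before, leans towards adding.

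The analysis also accepts patients with one epoch, so removing patients whole may be too harsh. This stands too: Step 4 shows power reaching about 0.92 at 30% hemorrhage. A reader might infer that the 21-dose rule settles the matter by making everyone who stops drug at a hemorrhage noncompliant. The documents do not go that far. Section 9.3.2 names patients who stop drug and noncompliant patients as separate groups, and the compliance text does not say whether days after a protocol-directed stop count as missed doses. The treatment of those patients' earlier epochs is open.

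A reader might also infer that 37.5% can be reached only by counting half the follow-up of patients who bleed. That is not so: with 3.5% intolerance and 20% hemorrhage, 0.9 × 0.9 × 0.965 × 0.8 = 0.625, a 37.5% loss. But this uses the lower hemorrhage figure, so it is not the highest case.

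Finally, a reader might fear that a factor of 1.375 would be re-applied at the midpoint. Section 9.3.4 describes re-estimating correlation and variance, anticipates no increase in sample size, and contains no such step.

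The SD of 30 is conservative. It is about 20% above the pilot value, so the pilot SD is near 25, and at 25 even 18 per arm would give power of about 0.91. That is not, however, the assumption on which the plan states its power.

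**Conclusion.** The point holds as one of unsupported statements and mislabelled arithmetic. At the upper limits listed in 9.3.2 the combined loss is 46% to 55%, not 37.5%. With lost patients removed whole, about 18 to 21.5 per arm remain, with power about 0.79 to 0.86. Over the full 20-30% hemorrhage range the figures are about 18 to 25 per arm and 0.79 to 0.90. If all patients who bleed keep year 1, power at 30% hemorrhage is about 0.89 to 0.92.

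The tempting stronger conclusion, that 0.90 power will not be delivered, does not follow. It depends on how losses overlap, when hemorrhages occur and how epochs after drug stop are handled, none of which the plan specifies. Noncompliance, which the synopsis says is covered, has no rate; any loss from it beyond the listed causes would lower these figures.

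The expansion wording is wrong regardless of those assumptions. The enrolled number of 40 per arm is correct for a 37.5% loss, and primary intention-to-treat power is untouched. All power figures assume the plan's own SD, correlation and difference, and equal losses in the two arms.

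**What to change.** In the synopsis, 9.3.1 and 9.3.2, say that 40 per arm allows for a 37.5% loss (25/0.625, a 60% expansion), in place of an expansion by 37% or 37.5%.

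Either show how 37.5% was derived, including the overlap assumed, or remove the claim that it is the highest combined estimate and the assurance of 25 per arm.

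Restate treatment-rendered power as a range: about 18 to 25 patients per arm and power about 0.79 to 0.90 with whole-patient loss, and up to about 0.92 at 30% hemorrhage if year-1 epochs of patients who bleed are retained. Next to the range, state which epochs count after drug stop, whether doses not taken after a protocol-directed stop count as missed, and the noncompliance rate assumed.

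The cost is wording and a less favourable power statement for one secondary analysis. No patients are added and the primary design does not change.

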#### **9.3.4 Adaptive Adjustments to Sample size**

In addition to looking at the futility of the treatment effect, we will also assess the actual within person correlation in the year 1 and year 2 outcome measures, and the variance in the change scores within each arm. Since the sample size is strongly related to these two statistics, estimating the true correlation and variances will allow us to propose adjustments to the sample size at the midpoint of the trial. **A larger than expected correlation and/or a smaller than expected variance of the change scores will allow us to reduce the final sample size but still retain the same estimated power.** We do not anticipate projecting a higher sample size than initially proposed, given our conservative assumptions regarding the within person correlation in the year 1 and year 2 outcome measures and variance in the change scores.

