#### **9.4.1 Data and Safety Monitoring Team**

The data and safety monitoring team was discussed and approved by the NINDS staff. It will comprise the local IRB, the trial's safety compliance officer (SCO) (Section 10.3.2), and an IMSM from outside the study and data management institutions, assisted by two external medical safety consultants with expertise in CCM disease and in statin therapy respectively. The data and safety monitoring team will provide an ongoing review

of the research, adjudicating adverse events, performing interim safety and efficacy analyses, and assessing progress towards achieving the goals of the study.

Safety assessment will take place at the end of the first year, after 30 participants have completed 12 months of follow-up and again after 60 subjects have completed 12 months of follow-up. Additional reviews will be decided on an ad hoc basis based on the frequency of safety endpoints encountered during the trial. The Brain Injury Outcomes (BIOS) statistician will provide the IMSM and the PI relevant tables including information regarding demographics, rebleeding rates, AEs, SAEs, and radiological and laboratory abnormalities (CT scans, liver function, etc.), per treatment assignments labeled A and B without unblinding. In addition, the IMSM will be provided with a copy of the SAE forms received. Further information will be given to the IMSM upon his/her request. The IMSM will provide written recommendation as to whether the study may continue, possible amendment(s) to the protocol, or whether the study should be stopped. The final decision will rest with the study PI, guided by protocol mandated safety thresholds to suspend and potentially revise or stop the trial (see below). Any protocol revision would require approval by the IRB, and shall be discussed with NINDS staff and external consultants prior to implementation.

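### Section 9.3.4 reverses the effect of the within-person correlation: for the planned time-averaged difference, a larger correlation raises the required sample size.

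*Combined protocol and SAP*

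**What the plan says.** Section 9.3.1 states that the evaluation of the primary outcome "will be performed as a time-averaged difference between two arms using a repeated measures analysis", with two annual percent-change scores per patient. The pilot's within-person correlation was "estimated at approximately -0.6 (Spearman); however, as this was based on only 6 patients" with two years of data, so "we chose the more conservative within person correlation of 0 for our sample size estimates". The SD of 30 is one "which to be conservative is about 20% larger than the standard deviation in our pilot data". On these inputs the plan requires 25 patients per arm for a 20-point difference at 90% power, and 44 or 17 for 15 or 25 points. It enrols 40 per arm.

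Section 9.3.4 covers the midpoint look at the correlation and the variance. Its rule, printed in bold, is: "A larger than expected correlation and/or a smaller than expected variance of the change scores will allow us to reduce the final sample size", at unchanged estimated power. It adds that no increase is anticipated, "given our conservative assumptions regarding the within person correlation in the year 1 and year 2 outcome measures and variance in the change scores". It gives no formula and no cut-off.

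**The concern.** Sections 9.3.1 and 9.3.4 imply opposite directions for the same analysis. Zero is more conservative than −0.6 only if the required number rises with the correlation. Section 9.3.4 has it fall.

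Section 9.3.4 is the passage that would guide a resizing proposal, and its and/or wording lets the correlation alone justify a cut. If a positive correlation were seen with the SD near 30, the rule would shrink the trial when the plan's formula asks for more patients, and the claim of unchanged power would be false.

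The expectation of no increase has the same weakness. An assumed correlation of 0 is conservative only against negative values, and the single negative estimate comes from six patients.

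**Working it through.** **Inputs.** From Section 9.3.1: two measures per patient, SD 30, ρ = 0, two-sided α 0.05, power 0.90, difference 20 (also 15 and 25), pilot ρ about −0.6. The pilot SD is implied as 30/1.2 = 25. From Section 9.3.2: 10% imaging loss, and "We further project an additional 10% missing data due to imperfect follow-up".

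**Formula.** For two scores with common SD and correlation ρ, the variance of the patient's average is SD²(1+ρ)/2. With complete pairs, the comparison of arms is a two-sample t comparison of these averages. Approximately,

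n per arm = 2(z₀.₉₇₅ + z₀.₉₀)² × [SD²(1+ρ)/2] / Δ².

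**Reproducing the plan.** At ρ = 0 the variance is 900/2 = 450. For Δ = 20, n = 2 × 10.51 × 450/400 = 23.6, so 24 by the normal approximation. The noncentral t (2n−2 degrees of freedom) gives 25. For Δ = 15 and 25 it gives 44 and 17. All three match the plan exactly, so its sample size follows this formula.

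**Varying ρ at SD 30, Δ = 20 (noncentral t).** The 25 evaluable is 40 × (1 − 0.375), the plan's full allowance. The 32 evaluable is 40 × 0.80, taking the 10% + 10% loss as per patient.

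| ρ | 900(1+ρ)/2 | Evaluable need per arm | Power, 25 evaluable | Power, 32 evaluable |
|---|---|---|---|---|
| −0.6 | 180 | 11 | >0.99 | >0.99 |
| 0 | 450 | 25 | 0.90 | 0.96 |
| 0.3 | 585 | 32 | 0.82 | 0.90 |
| 0.4 | 630 | 35 | 0.79 | 0.88 |
| 0.5 | 675 | 37 | 0.76 | 0.86 |

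At SD 30, enrolling 40 per arm keeps 90% power up to ρ of about 0.31 with 20% loss, but only to about 0 with 37.5% loss.

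**Offset by a smaller SD.** The variance half of the rule is right. Twenty-five evaluable per arm still suffices if the SD is at most about 26.5 (ρ = 0.3), 25.5 (ρ = 0.4) or 24.6 (ρ = 0.5). At SD 25 the need is 18, 24 and 26 at ρ = 0, 0.4 and 0.5, so 25 per arm is enough up to ρ of about 0.46.

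**Effect of a wrong cut (assumed example).** Suppose ρ = 0.4 is seen at SD 30 and enrolment stops at 32 per arm. With 20% loss, about 26 are evaluable and power is 0.80. Enrolling all 40 gives 32 evaluable and power 0.88.

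**The case against.** - **Reading.** If larger meant larger in magnitude, towards the pilot's −0.6, Section 9.3.4 would be true and would agree with Section 9.3.1. The text does not say this. Against an expected 0, a negative correlation is a smaller one.
- **Safeguards.** Section 9.3.4 speaks of proposing adjustments, Section 9.3.1 names the method, and under Section 9.4.1 "Any protocol revision would require approval by the IRB". A wrong cut would have to survive that review. This lowers the chance of harm but does not correct the rule.
- **A positive correlation may not appear.** The only estimate is negative. If each annual change runs from scan to scan, as in the pilot described in Section 2.2, the two scores share the 12-month scan with opposite sign, and measurement error pushes ρ down. Stable differences between patients push it up. If ρ is at or below 0, the sentence triggers no harmful cut.
- **Loss rate.** Section 9.3.2 ties the 37.5% expansion to the treatment-rendered analysis, and patients who stop drug stay in the primary analysis. For the primary analysis, 32 evaluable per arm is therefore the fairer case. At SD 25 it keeps power at about 0.95 even at ρ = 0.5.
- **Accrual.** Section 3.1 plans 12 + 10 + 5 = 27 patients a year. With uniform accrual and 20% loss, the 50 epochs set for the futility look in Section 9.3.3 arrive when 0.8 × 27 × (2t − 3) = 50, at t of about 2.66 years. About 72 of the 80 are then already enrolled. A cut at that point leaves 36 × 0.8, about 29 evaluable per arm, with power 0.85 against 0.88 at ρ = 0.4 and SD 30.

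The last three points stand as limits on the size of the harm. None of them makes the sentence correct.

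**Conclusion.** The concern holds. For the stated primary contrast, the correlation half of the Section 9.3.4 rule is reversed, and it contradicts Section 9.3.1. The computed sample size of 25 per arm is correct on its assumptions; the error lies in the resizing rule.

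How much it matters depends on what the midpoint shows. It does no harm if ρ is at or below 0, or if a smaller SD offsets a positive ρ. If ρ is positive and the SD stays near 30, any correlation-driven cut lowers power that may already be short of 90%. At ρ = 0.4 the loss is about 3 percentage points under the planned accrual, and 8 if enrolment stopped at 32 per arm. These figures assume complete pairs, a common SD in both years and arms, and 20% loss per patient.

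The expectation of no increase is not secured, because ρ = 0 protects only against negative correlations. The sentence should be corrected before the midpoint look.

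**What to change.** In Section 9.3.4, replace the bold sentence with wording such as:

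> A smaller (more negative) than expected correlation and/or a smaller than expected variance of the change scores will allow a reduction. A positive correlation raises the required number by the factor 1+ρ.

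Then:

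- State that resizing uses the Section 9.3.1 calculation with per-patient variance SD²(1+ρ)/2, entering the interim SD and correlation together and not as two separate reasons to cut.
- Qualify the no-increase sentence: ρ = 0 is conservative only against negative correlations, and the expectation holds only if a smaller SD offsets any positive ρ.
- If the re-estimated evaluable need exceeds the number expected to be evaluable (not the 40 enrolled), restate the achieved power.
- As a minor side point, reconcile the Synopsis, which bases the recalculation on the observed outcome and treatment effect, with Section 9.3.4, which names only correlation and variance.

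The cost is wording in Section 9.3.4 and one Synopsis sentence, plus IRB approval and the discussion with NINDS staff and external consultants that Section 9.4.1 requires. The plan would promise less in sample-size savings. It might also have to report power below 90% if ρ proves positive and the SD stays near 30.
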